### 2.1.6 Immunogenicity variables

All measurements (scheduled or unscheduled) will be assigned to analysis windows defined in Table 7, in order to provide an assessment of the ADA parameter at each time point planned to be collected as per protocol.

Anti-SAR156597 antibodies (ADA) samples are planned to be collected at approximately the same times as the PK samples, namely: Visit 2 (Day 1), Visit 4 (Week 4), Visit 6 (Week 12), Visit 7 (Week 24), Visit 8 (Week 36), Visit 9 (EOT visit at Week 52) and Visit 10 (EOS visit at Week 64).

ADA positive patients are patients with at least 1 treatment-induced or treatment-boosted ADA positive sample during the TEAE period, where

- Treatment induced ADAs: ADAs developed de novo (seroconversion) following administration of the biotherapeutic (i.e., formation of ADAs any time after the initial drug administration in a subject without pre-existing ADAs). If the baseline ADA sample is missing or non-reportable and at least one reportable ADA sample is available during the treatment (including follow-up period) the baseline sample will be considered as “negative” for data analysis. This is considered being a conservative approach for ADA assessment.
- Treatment boosted ADA: Pre-existing ADAs that were boosted to a higher level following administration of biotherapeutic (i.e., any time after the initial drug administration) the ADA titer is significantly higher than the baseline titer. A low serial dilution schema (2-fold or 3 fold) should be applied during titration. A difference in titer values of two titer

steps between an on treatment or follow-up sample and its baseline sample is considered significant. For examples, at least a 4-fold increase in titers for 2-fold serial dilution schema (or 9-fold increase in titers for 3- fold serial dilution schema). If no titer could be determined for a positive sample, the titer will be reported as the MRD of the assay.

The rest will be classified as ADA negative or inconclusive patients.

The following variables will be described:

- ADA response (Positive, Negative or inconclusive). For ADA positive:
  - Titer levels
  - Neutralizing status (Positive or inconclusive)
- Pre-existing positive ADA defined as patients with positive ADA response at baseline with less than a specific increase (depending on titer calculation, e.g. 4-fold increase in titer for 2-fold serial dilution schema, 9-fold increase in titer for 3-fold serial dilution schema) in the post-baseline period
- Treatment-emergent positive ADA response defined as 1) Patients with no ADA positive response at baseline but with any positive response in the post-baseline period (up to follow-up visit) or 2) Patients with a positive ADA response at baseline and at least a specific increase (depending on titer calculation, e.g. 4-fold increase in titer for 2-fold serial dilution schema, 9-fold increase in titer for 3-fold serial dilution schema) in titer in the post-baseline period (up to follow-up visit). For treatment-emergent positive ADA, the following categories for ADA duration will be applied:
  - A persistent positive response is a treatment-emergent ADA positive response detected in at least 2 or more post-baseline samples separated by at least a 16-week period (irrespective of any negative sample in between)
  - An indeterminate duration positive response is defined as ADA present only at the last sampling time point (and all previous samples negative) or with two last samples are positives but separated by a period less than 16 weeks.
- A transient positive response is defined as
  - Treatment induced ADA detected only at one sampling time during treatment or follow-up observation period (excluding last sampling time)
  - Treatment induced ADA detected at two or more sampling time during treatment where the first and last ADA positive sample are separated by a period less than 16 weeks and last sampling time is negative.
- Duration of ADA defined as longevity of treatment induced ADA (in days): date of last treatment induced ADA sample minus date of first treatment induced or treatment boosted ADA sample + 1. This will be calculated only for subjects with at least 2 positive ADA samples.
- Time to onset of treatment-emergent ADA positive response (in days): date of first ADA positive – date of first IMP administration.

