Archive blood samples (protein and mRNA biomarkers) ^v		X								X							X			
Blood DNA for genomics ^w		X																		

- a Randomization/baseline Visit is defined as Day 1. Visit windows for subsequent visits are +/- 2 days.
- b All assessments at Visit 2 (Day 1) are to be conducted predose with the exception of the assessment of local tolerability of SC injections.
- c Supplementary calls may be made to supply IMPs kits directly to patient's home.
- d Study treatment to be administered once a week, either at the site level or at home by a nurse.
- e Complete physical examinations will include skin, nasal cavities, eyes, ears, respiratory, cardiovascular, gastrointestinal, neurological, lymphatic and musculoskeletal systems. [REDACTED] Nail beds (periungual areas) should be examined for "splinter lesions" and digital tuft for tuft purpura or ischemia. Gynecological and urogenital examinations will not be done in this study unless for cause.
- f Vital signs, including blood pressure (mmHg), heart rate (beats per minute) and body weight (kg) will be measured at screening, baseline and every subsequent visit. Height (cm) will be measured at screening (Visit 1) only. BMI will be calculated automatically at all visits.

- g* Hematology: Hemoglobin, hematocrit, red blood cell count, erythrocyte sedimentation rate (ESR), white blood cell count with differential and platelet count. Biochemistry: Fasting glucose, blood urea nitrogen, creatinine, sodium, potassium, chloride, bicarbonate, calcium, phosphorous, total protein, albumin, total bilirubin, alkaline phosphatase, ALT, AST, CPK, hs CRP. Urinalysis (dipstick) to include: specific gravity, pH, glucose, ketones, blood, protein, nitrate, leukocyte esterase, urobilinogen and bilirubin. If any parameter on the dipstick is abnormal, a urine sample should be sent to the central laboratory for testing. If positive for proteins, microscopic analysis is performed by central laboratory.
- h* Serology testing includes hepatitis B surface antigen, hepatitis B surface antibody, hepatitis B core antibody, and hepatitis C antibodies.
- i* [REDACTED]
- j* Tuberculosis screen: history and QuantiFERON-TB Gold test. If result of QuantiFERON-TB Gold test is indeterminate, the test should be repeated.

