#### 2.4.7 Analyses of immunogenicity data

The following summaries will be performed on the ADA population, taking into account all samples regardless of timing in relation to injections:

- ADA results (negative, positive or inconclusive) by time point and by treatment arm
- Neutralizing status (inconclusive or positive) for positive ADA by time point and by treatment arm
- ADA titers using descriptive statistics (median, Q1, Q3, minimum and maximum) for positive ADA by time point and by treatment arm
- Number (%) of patients with pre-existing ADA and number (%) of patients with treatment-emergent ADA positive response by treatment arm
- Number (%) of patients with persistent/transient/indeterminate treatment-emergent ADA positive response by treatment arm
- Time to onset of treatment-emergent ADA positive response (in days) using descriptive statistics by treatment arm and also according to peak titer.
- Duration of ADA (in days, only for subjects with at least 2 positive ADA samples) using descriptive statistics by treatment arm.

Correlations between ADA parameters (eg, titers, treatment-emergent ADA positive status, neutralizing status) and PK, safety and/or main efficacy endpoint(s) will be explored (eg, scatter plot) according to the study results.

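### Treatment-boosted patients count as treatment-emergent ADA, but the SAP's onset, duration and duration-class definitions do not handle them consistently

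*SAP*

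**What the plan says.** SAP section 2.1.6 defines a treatment-emergent response in two ways. The first is a positive sample after a non-positive baseline (induced). The second is "Patients with a positive ADA response at baseline and at least a specific increase" in titer afterwards (boosted, described as "Pre-existing ADAs that were boosted to a higher level following administration of biotherapeutic").

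Three variables are then derived:

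- **Onset:** "Time to onset of treatment-emergent ADA positive response (in days): date of first ADA positive – date of first IMP administration".
- **Duration:** introduced as the longevity of treatment-induced ADA, but computed as "date of last treatment induced ADA sample minus date of first treatment induced or treatment boosted ADA sample + 1", for subjects with two or more positive samples.
- **Class (persistent, indeterminate or transient):** stated to apply to treatment-emergent positive ADA. Persistent is worded for any treatment-emergent response. Indeterminate has two limbs: ADA at the last sample only, with every earlier sample negative; or the last two samples positive and less than 16 weeks apart. Both limbs of transient are confined to treatment-induced ADA.

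SAP section 2.4.7 tabulates all three by arm. Onset appears as "Time to onset of treatment-emergent ADA positive response (in days) using descriptive statistics by treatment arm and also according to peak titer", and the class counts are for treatment-emergent responses. Protocol section 11.4.3 applies the three classes to treatment-induced patients only. SAP section 1.5, which lists major changes to the protocol's statistical section, does not mention this widening.

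**The concern.** A boosted patient is positive at baseline by definition, and the onset formula does not say that the first positive sample must be post-baseline or boosted. The duration formula names boosted samples at its start but not at its end. The class rules take in boosted patients through the treatment-emergent scope, then close transient and one limb of indeterminate to them.

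Immunogenicity is a secondary objective (protocol section 5.2, SAP section 1.2.2). If programmed as written, the onset table would mix true onset times with zeros that carry no information, the duration table would silently drop boosted patients, and the three class counts could fall short of the treatment-emergent count in the same set of outputs.

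**Working it through.** The documents give no figure for ADA onset, duration or class, so there is none to reproduce. The check applies the definitions to the planned sampling days.

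**Inputs**

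- ADA target days from SAP Table 7 and the Day 1 baseline: 1 (baseline), 29 (W4), 85 (W12), 169 (W24), 253 (W36), 365 (W52), 449 (W64).
- The baseline sample is at Visit 2, Day 1: "samples are planned to be collected at approximately the same times as the PK samples, namely: Visit 2 (Day 1), Visit 4 (Week 4"). It precedes dosing: "All assessments at Visit 2 (Day 1) are to be conducted predose" (protocol section 1.2, flow chart notes).
- 16 weeks = 112 days.

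**Onset**

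Literal formula: "date of first ADA positive – date of first IMP administration". For a boosted patient this is Day 1 − Day 1 = 0 days, whether the boost appears at W4 or W64. Dated from the first boosted sample, the values are 29 − 1 = 28, 85 − 1 = 84, 169 − 1 = 168, 253 − 1 = 252, 365 − 1 = 364 or 449 − 1 = 448 days.

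**Duration**

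Take a patient boosted from W24 to W52. The start date exists (Day 169). The end date is the last treatment-induced sample, and a patient with pre-existing ADA has none, so the result is undefined even though the two-positive-samples condition is met. If boosted samples counted at both ends, the value would be 365 − 169 + 1 = 197 days.

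**Class**

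Six post-baseline visits give 2^6 − 1 = 63 non-empty patterns of qualifying samples. For boosted patients, only samples meeting the titer-rise rule are counted as qualifying.

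- Gaps between adjacent visits are 56 (W4–W12), 84 (W12–W24), 84 (W24–W36), 112 (W36–W52) and 84 days (W52–W64). The shortest span of three visits is W4–W24, 169 − 29 = 140 days.
- The patterns that do not span 112 days are therefore the 6 single visits and 4 pairs: W4+W12, W12+W24, W24+W36 and W52+W64. The other 63 − 10 = 53 are persistent.
- Induced: W64 alone and W52+W64 are indeterminate (2); the remaining 5 singles and 3 pairs are transient (8).
- Boosted: W52+W64 is indeterminate through the second limb (1). The 6 singles and the other 3 pairs have no class (9), because transient is induced-only and the positive baseline rules out the first indeterminate limb.

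| Class | Induced patterns | Boosted patterns |
|---|---|---|
| Persistent | 53 | 53 |
| Transient | 8 | 0 |
| Indeterminate | 2 | 1 |
| No class | 0 | 9 |
| Total | 63 | 63 |

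These are counts of possible patterns, not expected patient frequencies.

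**The case against.** The best defence is that the intent can be recovered. The onset variable is named for the treatment-emergent response. SAP section 2.1.6 ties ADA-positive status to an induced or boosted sample in the TEAE period, and SAP section 2.1.4 starts that period at the first IMP administration, so a pre-dose sample lies outside it. The adjacent duration formula even names the right start sample. All of this makes it probable that onset was meant to run from the first treatment-emergent sample. It does not correct the formula, which asks only for the first ADA positive in a section that itself calls a baseline result positive. A programmer who follows it gets 0.

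On duration, the label limits the variable to treatment-induced ADA, so having no value for boosted patients could be deliberate. That is a fair reading, but the start date then should not mention boosted samples. The sentence contradicts its own label whichever scope was meant.

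On class, a reader might infer that boosted patients have no class at all. The rules do not support that: 54 of the 63 boosted patterns (53 + 1) are classified. A reader might also infer that unchanged pre-existing positivity at every visit would count as persistent. The rule requires a treatment-emergent response in the separate samples, and its natural reading excludes samples without the titer rise.

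It is also true that the consequence is small. No test, efficacy endpoint or count of treatment-emergent patients changes.

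**Conclusion.** The definitions are wrong as written, in three limited ways:

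- literal onset is 0 days for every boosted patient with the planned Day 1 sample;
- duration has start and end terms that do not match, and gives no value for boosted patients;
- boosts seen at a single visit, or only at W4+W12, W12+W24 or W24+W36, have no class, so class counts need not sum to the treatment-emergent total.

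The count of 9 in 63 assumes samples on the planned days and counts only those meeting the titer-rise rule.

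A reader might go further and infer a definite shift in mean or median onset, or a spurious link between early onset and high peak titer. The documents support neither. They do not give the number of boosted or induced patients, and the boosted number could be zero. They set no peak-titer cut-offs, and a boost from a minimal baseline titer can still end low. No size of bias is claimed. The effect is confined to descriptive immunogenicity tables.

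**What to change.** Reword three definitions in SAP section 2.1.6:

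1. **Onset:** the date of the first post-baseline treatment-induced or treatment-boosted sample minus the date of first IMP administration. For a boosted patient this is the first sample meeting the titer-rise criterion.
2. **Duration:** use the same sample type at both ends, either induced or boosted for both, or induced only for both, and make the label agree.
3. **Class:** either restrict the three classes to treatment-induced patients, as in protocol section 11.4.3, and show boosted patients on their own row; or keep the treatment-emergent scope and extend transient and indeterminate to samples meeting the titer-rise criterion. Extending them classifies all 63 patterns. If the wider scope is kept, record it in SAP section 1.5 as a change from the protocol.

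Adjust the row descriptions in SAP section 2.4.7 to match. The cost is a few lines of text and the matching program specification; no new data or samples are needed.

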### 2.1.7 Biomarker endpoints

All measurements (scheduled or unscheduled) will be assigned to efficacy analysis windows defined in [Table 6](#), in order to describe all BM assessments by time points even in case of premature treatment discontinuation.

Peripheral blood are planned to be collected for measurement of protein biomarkers in serum or plasma at the study visits 2 (Day 1), 7 (Week 24) and 9/EOT (Week 52).

The protein biomarkers include, but are not limited to:

- Inter-cellular adhesion molecule 1 (ICAM1),
- TARC,
- Periostin,
- Human Epididymis protein 4 (HE4).
- IL-6

### 2.1.8 Health economic endpoints

Health economic endpoints other than quality of life will not be assessed.

## 2.2 DISPOSITION OF PATIENTS

This section describes patient disposition for both patient study status and the patient analysis populations.

Screened patients are defined as any patients who signed the informed consent.

Randomized patients consist of all patients with a signed informed consent form who have had a treatment kit number allocated and recorded in the IVRS/IWRS database, regardless of whether the treatment kit was used.

For patient study status, the total number of patients in each of the following categories will be presented in the clinical study report using a flowchart diagram or summary table by treatment arm and overall:

- Screened patients
- Screen failure patients and reasons for screen failure
- Non-randomized but treated patients
- Randomized patients
- Randomized but not treated patients and reason for not being treated
- Randomized and treated patients

- Patients who complete and did not complete the study treatment period as per protocol
- Patients who discontinued study treatment by main reason for permanent treatment discontinuation
- Patients who complete and did not complete the study follow-up period as per protocol
- Patients who discontinued study by main reason for study discontinuation
- Status at last study contact and patient ongoing at the moment of the early analysis

This table will be duplicated for background therapy status.

For all categories of patients (except for the screened and non-randomized categories) percentages will be calculated using the number of randomized patients as the denominator. Reasons for treatment discontinuation will be supplied in tables giving numbers and percentages by treatment arm. This summary will be provided by treatment arm.

The incidence of premature treatment discontinuation (irrespective of the reason) and premature treatment discontinuation due to AEs will be presented graphically by treatment arm, background therapy status on randomized and treated patients (as randomized), using Kaplan-Meier method. The time-to-event variable is defined as: event date – randomization date + 7 days, where an event could be:

- a permanent treatment discontinuation recorded on the “End of Treatment” eCRF page with a No answer to “Did the subject complete treatment period per protocol?”.
- a death before week 52 (without previous EOT) recorded on the “Death” eCRF page.

In case of a complete treatment period (with a Yes answer to “Did the subject complete treatment period per protocol?” recorded on the End of Treatment” eCRF page), the patient will be censored at the completion date.

The incidence of premature study discontinuation will be presented graphically by treatment arm, background therapy status on randomized patients, using Kaplan-Meier method. The time-to-event variable is defined as: event date – randomization date + 1 day, where an event could be:

- a study discontinuation without a 12-week follow-up.
- a study discontinuation with a 12-week follow-up but occurring before week 52.
- a death occurring before week 52 (without previous EOS) recorded on the “Death” eCRF page.

In case of a complete study period (i.e. with at least 12 weeks of follow-up ending after week 52), the patient will be censored at the completion date.

A patient is considered lost to follow-up at the end of the study if he/she is not assessed at the last protocol planned visit and if the time from the last successful contact (from the vital patient status case report form) to the last protocol planned visit is greater than 2 days, unless died before.

Patient with insufficient follow-up will be described.

A patient is considered with insufficient follow-up or without follow-up at the end of the study in the following cases:

- If the patient is not assessed at the scheduled follow-up visit, or any post-treatment visit, unless patient died before;
- If the follow-up visit is less than 12 weeks after the last double-blind IMP injection.

All critical or major quantitative deviations potentially impacting efficacy, randomization and drug-dispensing irregularities, and other important deviations will be summarized in tables giving numbers and percentages of deviations by treatment arm. These deviations are listed in the data review and surveillance plan. All critical or major qualitative deviations will be described.

Additionally, the analysis populations for safety, efficacy, pharmacokinetics, immunology and biomarkers will be summarized in a table by number of patients on the randomized population.

- Efficacy population: modified intent-to-treat (mITT) population
- Safety population
- Pharmacokinetics population
- Anti-Drug Antibody population
- Pharmacodynamics biomarker populations: Biomarker TARC population, Biomarker ICAM1 population, Biomarker HE4 population, Biomarker Periostin population, Biomarker IL-6 population.

Definitions of the study populations are provided in [Section 2.3](#).

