#### *Observation period*

The observation period will be divided as follows:

- The **pre-treatment** period is defined as the time from the signed informed consent date up to the first administration of IMP.
- The **treatment-emergent adverse event (TEAE)** period is defined as the time from the first administration of the IMP to the last administration of the IMP + 84 days. It will include both **treatment** and **residual treatment** periods:
  - The **treatment** period is defined as the time from the first administration of the IMP to the last administration of the IMP + 7 days
  - The **residual treatment** period is defined as the time from the last administration of the IMP + 8 days to the last administration of the IMP + 84 days.
- The **post-treatment** period is defined as the period of time starting the day after the end of the TEAE period (ie, 85 days after the day of last dose of double-blind IMP injection).

The on-study observation period is defined as the time from the first administration of IMP until the end of the study (defined as last protocol planned visit (end of study visit) or the resolution/stabilization of all SAEs and adverse events of special interest (AESIs)).

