#### **2.4.3.1 Extent of investigational medicinal product exposure**

The extent of IMP exposure will be assessed by the duration of IMP exposure.

Duration of IMP exposure is defined as last dose date – first dose date + 7 days, regardless of unplanned intermittent discontinuations (see [Section 2.5.3](#) for calculation in case of missing or incomplete data).

Duration of IMP exposure will be summarized descriptively as a quantitative variable (number, mean, SD, median, minimum, and maximum) in weeks. In addition, duration of treatment exposure will also be summarized categorically by numbers and percentages for each of the following categories and cumulatively according to these categories:  $\geq 1$  day and  $< 2$  weeks,  $\geq 2$  weeks and  $< 4$  weeks,  $\geq 4$  weeks and  $< 6$  weeks,  $\geq 6$  weeks and  $< 12$  weeks,  $\geq 12$  weeks and  $< 24$  weeks,  $\geq 24$  weeks and  $< 36$  weeks,  $\geq 36$  weeks and  $< 44$  weeks,  $\geq 44$  weeks and  $< 53$  weeks and  $\geq 53$  weeks. Non-integer values will be rounded to 1 decimal place.

Additionally, the cumulative duration of treatment exposure will be provided, defined as the sum of the duration of treatment exposure for all patients, and will be expressed in patient years.

The graphical representation of exposure to investigational product and time since randomization will also be displayed by treatment arm.

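### The Kaplan-Meier curve of treatment discontinuation due to AEs has no rule for stops and deaths from other causes, and the +7-day offset is stated for events but not for completers

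*SAP*

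**What the plan says.** SAP section 2.2 (Disposition of patients) plans Kaplan-Meier plots of premature treatment discontinuation for any reason, and also "premature treatment discontinuation due to AEs will be presented graphically by treatment arm" and background therapy status. The time variable for both is "event date – randomization date + 7 days, where an event could be" a permanent discontinuation recorded as such, or "a death before week 52 (without previous EOT) recorded on the" death page of the eCRF. The two curves share this one list. For those who finish treatment, "the patient will be censored at the completion date", with no offset stated.

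The companion curve for study discontinuation, in the same section, uses a different offset: "event date – randomization date + 1 day, where an event could be" one of its own listed events. Section 2.2 also plans a table of "Patients who discontinued study treatment by main reason for permanent treatment discontinuation". No competing-risk estimator is named, and no test is attached to the curves.

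**The concern.** There are two separate matters.

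- **Estimand of the AE curve.** A patient who stops for another reason, or dies of another cause, can no longer stop because of an AE. Censoring such patients treats them as if they could still have stopped for an AE later, so one minus Kaplan-Meier exceeds the proportion who actually stop for AEs. Counting every listed event instead reproduces the any-reason curve under another name. The SAP chooses neither.
- **Time scale.** If events carry +7 days and completers carry nothing, the two groups are on different clocks. Most completers leave the risk set close together around Week 52, so a late event plotted after them meets an almost empty risk set.

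These plots show by arm when, and why, patients come off drug. A false drop in the tail of one arm, or an inflated AE curve, could be read as a tolerability difference.

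**Working it through.** The documents give no numerical figure for these curves, so there is nothing to reproduce first. They also give no treatment discontinuation rate. The sample size raises 92 to 100 per arm, an allowance of (100 − 92)/100 = 8% for dropouts. The range of 8% to 50% total discontinuation used below is an assumption.

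**AE curve, if other stops are censored.** Let F be the total proportion stopping by Week 52 and s the share due to AEs, with the cause-specific hazards in constant ratio. The total cumulative hazard is H = −ln(1 − F), of which sH is for AEs. Then

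- one minus Kaplan-Meier = 1 − exp(−sH) = 1 − (1 − F)^s
- true AE incidence = sF

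For F = 25% and s = 1/2: H = 0.2877, sH = 0.1438, and 1 − exp(−0.1438) = 13.4%, against a true 12.5%.

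| AE stops | Other stops | F | s | 1 − KM | True | Excess (points) |
|---|---|---|---|---|---|---|
| 4% | 4% | 8% | 1/2 | 4.1% | 4% | 0.1 |
| 10% | 10% | 20% | 1/2 | 10.6% | 10% | 0.6 |
| 10% | 20% | 30% | 1/3 | 11.2% | 10% | 1.2 |
| 15% | 15% | 30% | 1/2 | 16.3% | 15% | 1.3 |
| 20% | 20% | 40% | 1/2 | 22.5% | 20% | 2.5 |
| 20% | 30% | 50% | 2/5 | 24.2% | 20% | 4.2 |

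**Offset, read literally.** The Week 52 target is Day 365 (SAP Table 6), and the visit window is ±2 days (protocol section 10.1). With Day 1 as the randomization day:

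- a stop or death on study day d is plotted at (d − 1) + 7 = d + 6;
- a completer on Day 365 is censored at 364, and one using the full +2 days at 366;
- so an event falls after the Day 365 completers only if d + 6 > 364, that is d ≥ 359, and after all in-window completers only if d ≥ 361.

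Worked example: 100 patients, 20 stops, 80 completers all at 364. After 19 stops the survival estimate is 81/100.

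- Last stop on Day 358: time 364, tied with the completers, who still count as at risk. Survival is 81/100 × 80/81 = 80/100, so the plotted incidence is 20%, which is correct.
- Last stop on Day 359: time 365, with one patient at risk. Survival is 81/100 × 0 = 0, so the plotted incidence is 100%.
- Same offset for completers: 20% wherever the last stop falls.

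Simulation (100 per arm, constant hazard, 4,000 runs per scenario) shows how far the tail effect depends on assumptions. At 8% to 40% discontinuation, an arm's curve reaches 100% in 7.7% to 27.6% of runs if completion varies by ±2 days, but in 3.2% to 11.0% if it varies by ±7 days. Before the last week there is no overstatement. At 20% discontinuation (±2 days), the height at Day 350 is 19.2% with the offset and 19.5% without it, because the curve is only delayed.

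**The case against.** The mismatch in offsets may be one of wording only. Elsewhere the SAP treats a censoring date as a kind of event date: Table 2 (disease progression) and Table 3 (mortality) list censored patients under the event-date column, so the formula covers them. The study-discontinuation curve has the same structure, an offset for events followed by censoring at a bare completion date, and nobody would read it as two clocks. The 7 days also have a basis. The treatment period "is defined as the time from the first administration of the IMP to the last administration of the IMP + 7 days", and "Duration of IMP exposure is defined as last dose date – first dose date + 7 days". If the event date means the last dose, a nominal Week 51 stop (Day 358) gets 364 days and ties with a Week 52 completer, with no collapse. Some completion dates may also fall well after Day 365: SAP Table 2 provides for last lung-function assessments after Day 375, and a single completer after Day 370 keeps the curve from reaching 100%.

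Most of this stands. A common offset may well be intended, and it would leave only a six-day shift against the +1 convention. But the text does not say so, does not define the event date as the last dose, and applies the formula to deaths, whose date is not a dosing date.

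On the AE curve, the SAP never says that other stops are censored, the excess is modest, and AE-related stopping is reported without this bias in the table by reason (section 2.2) and in the tables of TEAEs leading to discontinuation (section 2.4.5.1). That limits the consequence but does not supply the missing rule.

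**Conclusion.** The AE curve needs a rule and a different estimator. With other stops censored, the overstatement is about 0.1 to 4 points under assumed total discontinuation of 8% to 50% and a constant ratio of hazards. With them counted, the curve does not show AE-related stopping. The time formula needs to be stated for completers. On the literal reading the error is confined to the tail, from about Day 359.

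A reader might infer more than the documents support:

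- **That both curves overstate incidence throughout.** They do not. The any-reason curve has no competing-risk problem, since every stop and death is an event, and before the last week the offset delays the curve and makes it very slightly low.
- **That the curves will jump to 100% at some predictable rate.** That needs the literal reading together with assumed stopping rates and completion timing, none of which the documents give.
- **That the SAP prescribes censoring of non-AE stops.** It is silent.

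The effect is limited to descriptive plots. No test, type I error or sample size is touched, so this is a minor improvement.

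**What to change.** Amend SAP section 2.2 in two places.

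- **AE curve:** plot a cumulative incidence function (Aalen-Johansen) for discontinuation due to AEs, with non-AE stops and non-AE deaths as competing events. State which deaths count as AE-related. Keep Kaplan-Meier for the any-reason curve.
- **Time variable:** define it once as event or censoring date minus randomization date plus 1 day, for events and completers alike, and say which date counts as the event date for a discontinuation. State the same for the study-discontinuation curve, so that the two can be compared.

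The cost is a few sentences and a standard option in the planned SAS software. No new data are needed.
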